### **3.3. HANDLING OF DATA**

#### **3.3.1. Strata and Covariates**

The baseline SALT score group (<50, >=50) will be used a stratum in the planned primary efficacy models. The strata will not be used in the subset analyses.

#### **3.3.2. Examination of Subject Subsets**

The baseline SALT score group (< 50, >=50) and the subjects who treat the whole scalp will be used for subset analyses. The details of the subset analyses are given in the statistical analysis section.

#### **3.3.3. Multiple Testing and Comparisons**

There are no planned adjustments for multiple comparisons.

#### **3.3.4. Missing Data and Outliers**

For missing clinical assessments, the method of last observation carried forward (LOCF) will be used to impute values. The last non-missing value prior to the missing assessment will replace the missing values. For subjects who terminate early, missing assessment after the date of early termination will be replaced by the LOCF method.

#### **3.3.5. Imputation of Incomplete Dates**

A missing date is one in which the day, month or year are all unknown. For adverse events, if a date is missing entirely then the date will be set to equal Day 1.

An incomplete date is any date for which either the day, month or year is unknown, but all three fields are not unknown. An incomplete date occurs when the exact date an event occurred or ended cannot be obtained from a subject. For many of the analyses, a complete date is necessary in order to determine if the event should be included in the analysis (i.e., if the event is treatment-emergent) or to establish the duration of an event. In such cases, incomplete dates will be imputed.

To minimize bias, the project statistician will impute dates in a systematic, but reasonable manner. If the month/year is the same as the Day 1 month/year then the date will be set to the date of Day 1. In other cases, missing days will be imputed as the day component of Day 1; missing months/years will be imputed as the month/year of Day 1. For nonexistent dates occurring at the end of a month created by this imputation method, the first date of the next month will be used (e.g. Day 1 = 31JAN2017, incomplete date = XXFEB2017 -> imputed date = 01MAR2017).

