### 3.3.6. Definitions and Terminology

#### Day 1 (DB)

Day 1 (DB) is defined as the date of the initial study medication application as reported on the study medication usage page of the CRF.

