#### Adverse Event (AE)

An AE is any untoward medical occurrence in a subject administered a study medication(s) and which does not necessarily have a causal relationship with the study medication. An AE can therefore be any unfavorable and unintended sign or symptom associated with the use of a study medication (including an abnormal laboratory finding), whether related to the study medication. Thus, any new, clinically significant worsening of an existing sign, symptom or disease, should be considered an AE. Every new episode or clinically significant worsening of a chronic condition (*e.g.*, headaches, seasonal allergies, depression, or hypertension) should be reported as a separate AE, even if the condition is reported in the subject's medical history.

Treatment-Emergent Adverse Event (TEAE)

For the interim analysis of the DB treatment period, any recorded AE that occurs on or after the initiation of study medication and within 31 days after the date of Visit 10 or after the date of last DB dose of study medication will be considered treatment-emergent. For the OLE period analysis, an AE that occurs on or after the initiation of OLE study medication and within 31 days after the date of last dose of study medication will be considered treatment-emergent.

Treatment-emergent Laboratory Abnormalities

A treatment-emergent laboratory abnormality is defined as a result in which the baseline value is within normal laboratory limits and the post-baseline value is outside normal laboratory limits. If the relevant baseline assessment is missing, then any post-baseline value outside normal laboratory limits is treatment-emergent.

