#### **5.3.1. Adverse Events**

Adverse events will be mapped to a preferred term and system organ classification by Medical Dictionary for Regulatory Activities (MedDRA) version 22.0.

An overall summary will be presented which includes the number of TEAEs and the number and percentage of subjects who experienced at least one TEAE. This summary will also include:

- Any TEAE
- Any Serious TEAE
- Any Mild TEAEs
- Any Moderate TEAEs
- Any Severe TEAEs
- Any Related TEAEs
- Any TEAEs leading to discontinuation
- Any Related TEAEs leading to discontinuation

Additional summaries of TEAEs will be provided showing the number and percentage of subjects who experienced at least one TEAE. These summaries will be presented by system organ class (SOC), preferred term (PT) and maximum severity. If a participant reports the same PT multiple times within the same SOC, that PT will only be counted once within that SOC for that participant. As with the PT, if a participant reports multiple conditions within the same SOC, that SOC will only be counted once for that participant. In the summary, SOC will be listed in ascending alphabetical order; PTs will be listed in order of descending frequency for all participants within each SOC.

The occurrence of TEAEs related to study medication (possibly/probably) will be tabulated by SOC, PT and maximum severity. Serious adverse events (SAE) will be presented by system organ class (SOC), preferred term (PT) and maximum severity. SAE related to study medication will also be presented by SOC and PT.

All AEs reported will be listed by individual subject, showing both verbatim and preferred terms. All AEs reported with a start date prior to the initiation of study medication will be excluded from the TEAE tables but will be included in the listings.

Missing onset dates will be imputed as previously outlined in Section 3.3.5 as required to determine TEAEs.

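### SAP 3.3.5 fills every missing date part from an unqualified Day 1 with no consistency checks, so some adverse events with month, year or whole date missing fall out of the TEAE tables or the OLE period

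*SAP*

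**What the plan says.** SAP 3.3.5 has three rules.

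- An adverse event date with nothing known: "if a date is missing entirely then the date will be set to equal Day 1".
- A partial date in the starting month: "If the month/year is the same as the Day 1 month/year then the date will be set to the date of Day 1".
- Any other partial date: "missing days will be imputed as the day component of Day 1; missing months/years will be imputed as the month/year of Day 1". If this gives a calendar date that does not exist, the first of the following month is used.

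The section covers both onset and end, since it speaks of cases where the "exact date an event occurred or ended cannot be obtained". It has no separate rule for end dates. Nothing in it refers to the last dose, to the period in which the event was recorded, or to the order of onset and end.

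SAP 3.3.6 defines two Day 1s. Day 1 (DB) is the "date of the initial study medication application"; Day 1 (OLE) is the Visit 10 date. SAP 3.3.5 says only Day 1. The Study Day formula in 3.3.6 uses the bare term for the DB date, so that is the natural reading here too.

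The imputed dates matter because of SAP 5.3.1: "Missing onset dates will be imputed as previously outlined in Section 3.3.5 as required to determine TEAEs". By SAP 3.3.6 the DB treatment-emergent window runs from first application to 31 days after Visit 10 or last DB dose. An OLE TEAE is "an AE that occurs on or after the initiation of OLE study medication", up to 31 days after the last dose. Events dated before first application are listed but left out of the TEAE tables (SAP 5.3.1). In the pooled display, subjects randomized to vehicle contribute only their OLE events (SAP 5.3.4).

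**The concern.** Borrowing date parts from Day 1 looks conservative, because it seems to pull uncertain onsets toward the start of treatment. That holds when only the day is missing, or when everything is missing in the DB period. It fails when the month or year is missing and the course runs into a second calendar year. The borrowed parts then move the event a year forward or a year back, out of the treatment-emergent window. It also fails in the OLE, where the reference date belongs to the wrong period.

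Safety is part of the primary objective. At stake is whether an event that began on treatment is counted as treatment-emergent, and whether an event that began on open-label drug is counted in the OLE and pooled tables.

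**Working it through.** **Inputs.** The rule and windows are those described above. Visit 10 is on Day 169 (schedules of assessments). Assumptions: Day 1 falls on each date of 2018 in turn; the DB course is complete (Days 1 to 169); OLE entry is at Visit 10, with 168 OLE days. The percentages are shares of possible date combinations given a missingness pattern. They are not expected event counts.

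**1. The SAP's own example.** Day 1 is 31 Jan 2017 and the incomplete date is February 2017. Borrowing day 31 gives 31 February, which does not exist, so the result is 1 Mar 2017. This reproduces "Day 1 = 31JAN2017, incomplete date = XXFEB2017 -> imputed date = 01MAR2017". The imputed date already lies outside the known month.

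**2. One DB subject.** Day 1 is 10 Nov 2018.
- Visit 10 = 10 Nov 2018 + 168 days = 27 Apr 2019. The window closes 31 days later, on 28 May 2019.
- Onset known only as 2019 becomes 10 Nov 2019, study day 365 + 1 = 366. That is after the window.
- Onset 14 February, year unknown, becomes 14 Feb 2018. That is before first dose.
- On-treatment days in 2019: 31 + 28 + 31 + 27 = 117 of 169, or 69%. An event on any of them is lost under either pattern.

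**3. Averaged over Day 1.** If j days of the year remain after Day 1, then 168 − j on-treatment days fall in the next year (j = 0 to 167; none otherwise).
- Sum: 168 × 169 / 2 = 14,196.
- Combinations: 365 × 169 = 61,685.
- Share: 14,196 / 61,685 = 23.0%.

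With month and day missing, each of these events moves to Day 366, beyond the last window day (169 + 31 = 200). With only the year missing, each moves back 365 days, to before Day 1. A course crosses the year end when Day 1 is 17 July or later (17 July + 168 days = 1 January).

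A missing month with the day known gives 23.0% or 56.8%, depending on whether the same-month rule is applied after or only before filling. The point does not rest on that unusual pattern.

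With only the day missing, none of the 61,685 is lost. For early discontinuers the imputed date is at most 30 days past the last dose, still inside 31. A missing day does push out 15.4% of events that begin 1 to 31 days after Visit 10.

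**4. OLE onsets, reading Day 1 as DB.**

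| Missing | Result | Share |
|---|---|---|
| Whole date | dated to DB Day 1 | 100% |
| Month and day | dated into the DB period | 30.8% |
| Day only | dated into the DB period | 1.9% |
| Year only | dated before DB Day 1 | 69% |

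The second row: an OLE event in the same calendar year as Day 1 is set to Day 1. The count is 14,196 + 28 × 168 = 18,900, out of 365 × 168 = 61,320.

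Example: Day 1 is 5 Nov 2018, and Visit 10 and OLE entry are on 22 Apr 2019. An OLE event recorded as April 2019 becomes 5 Apr 2019, 17 days before OLE drug. It is not an OLE TEAE. If the subject was randomized to vehicle, it also leaves the pooled display.

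**5. End dates.** Day 1 is 5 Nov 2018, onset 20 Feb 2019, end February 2019. The end becomes 5 Feb 2019, 15 days before onset. With the end day missing, this reversal occurs in 50% of combinations for a same-day event, 30% at 7 days, 15% at 14 days and 0.2% at 28 days. With end month and day missing it occurs in 69% to 76%.

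**The case against.** **The missingness is unlikely.** Events are elicited at every visit by asking about change since the last one (Protocol 9.2.1), DB visits are one to four weeks apart, and data queries are resolved before lock (Protocol 12.3). A year-only onset should be rare, and the commoner day-only gap loses no on-treatment DB event. All events stay in the listings. This stands, and it limits the size of the point.

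**Day 1 may mean Day 1 (OLE) for OLE events.** The text allows this but does not say it. It would remove the shift to before Visit 10, except when the year is missing (23%). It would not settle the matter, because Day 1 (OLE) is Visit 10 and not first OLE dose. SAP 5.2.9 provides for entry gaps of 60 days or more, and in those subjects a wholly missing onset would still precede OLE drug. The DB losses and the end-date reversals do not depend on this reading.

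**The end-date fault reaches no planned output.** TEAE status depends on onset, and SAP 8.1 and 8.2 list no duration table. This stands: only derived durations are affected.

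**A stronger reading is tempting.** A reader might infer that the rule systematically hides active-drug events or shifts them to vehicle. The documents do not support that. The year-end loss depends on start date and event date, not on arm. The DB window also overlaps early OLE treatment. Take a vehicle subject with Day 1 on 10 Nov 2018, OLE drug from 20 May 2019, and an event recorded as May 2019, imputed to 10 May. The DB window is open to 28 May, so any true onset from 1 to 28 May is a DB TEAE with or without imputation. Imputation decides only OLE and pooled status. Moreover, 19 of the 31 possible dates precede OLE drug, so an error arises only if the event really began afterwards.

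**Conclusion.** The rule is written out, and applied literally it gives wrong dates. On-treatment DB events in any arm can drop out of the TEAE tables when month or year is missing and treatment crosses a year end. The share is 23.0% of date combinations for either main pattern, averaged over Day 1 in 2018. The year-end condition is realistic: Protocol Version 7.0, which first admitted adolescents, is dated 10 Aug 2018, and any full course started from then to 31 December 2018 crosses it.

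OLE onsets that are wholly or partly missing can be dated before OLE drug. They are then not OLE TEAEs, and for vehicle-randomized subjects they are lost from the pooled display. This part rests on reading Day 1 as the DB date or, under the OLE reading, on a missing year or a gap before OLE entry.

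The number of events is probably small; the documents do not say how often dates are incomplete. No bias between arms in the DB comparison is shown. This is a minor point, worth correcting because correction is cheap.

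**What to change.** Replace the rule in SAP 3.3.5 with the following.

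- **Partial onset.** If the known parts are compatible with the first-dose date of the period in which the event was recorded (DB or OLE), impute that date. Otherwise impute the earliest date consistent with the known parts.
- **Limits.** Never impute outside the range the known parts allow, or after a known end date. Serious events are collected from consent (Protocol 9.1.4), so one dated October 2018 in a subject first dosed on 10 Nov 2018 must stay pre-treatment.
- **Missing year.** Choose the year that places the event in the recorded period.
- **Wholly missing onset.** Use the first dose of the recorded period.
- **Partial end date.** Use the latest consistent date, not before onset.
- **Reference dates.** Use actual first-dose dates, not Day 1 (OLE).

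A close variant (earliest consistent date, floored at the start of the recorded period) was run on the same combinations. It gives the same onset dates as this rule for events that truly began on or after the period start. With day, month and day, year or the whole date missing, it left 0% of on-treatment DB events dropped and 0% of OLE events dated before Visit 10. With the end day missing, it left 0% of end dates before onset.

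The cost is one SAP paragraph and some programming. No new data are needed, assuming the adverse event record shows the period in which each event was reported. The change is best made before the DB data are unblinded.

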### 3.3.6. Definitions and Terminology

#### Day 1 (DB)

Day 1 (DB) is defined as the date of the initial study medication application as reported on the study medication usage page of the CRF.

#### Day 1 (OLE)

Day 1(OLE) is defined as the date of the Visit 10 assessment for all subjects entering the OLE period.

#### Study Day

Study Day is defined relative to Day 1(DB). Thus, the study day of an event is calculated as:

Study Day = ((event date – date of Day 1(DB)) + 1) for dates on or after Day 1(DB)

Study Day = (event date – date of Day 1) for dates prior to Day 1(DB)

#### Period Day

Period Day is defined separately for the DB and OLE periods. Period day will be relative to the defined Day 1 of each period.

#### Study Visit

Study Visit is the nominal visit as recorded on the CRF.

#### Days on Study

Days on Study is calculated as: study discontinuation date - informed consent date + 1

#### Last Dose of Study Medication

Last Dose of Study Medication is defined as the last date that the subject applied study medication as determined by last date of recorded on the study medication usage page of the CRF.

#### Study Medication Exposure (days) in DB

Study drug exposure is defined as the (date of last DB dose – date of first dose + 1).

#### Dose Interruptions

Dose interruption is defined as 2 or more consecutive days where ‘None’ was checked for the number of applications per day field on the study medication page of CRF.

#### Missed Dose

A missed dose is defined as a single day where ‘None’ was checked for the number of applications per day field on the study medication page of CRF.

#### Study medication compliance (%) based on number of applications

The compliance with the dosing regimen will be calculated based on the subject-specific application regimen as, [(study medication exposure days - number of days with less than the subject-specific expected number of applications) / (study medication exposure days)] x 100.

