5.9. Subject Withdrawal Criteria

Subjects will be informed that they are free to withdraw from the study at any time and for any reason. The investigator may remove a subject from the study if, in the investigator's opinion, it is not in the best interest of the subject to continue the study. Examples of other reasons subjects may be discontinued from the study are: a change in compliance with an inclusion or exclusion criterion, occurrence of AEs, occurrence of pregnancy, use of a prohibited therapy or subject is unwilling or refuses to continue with the protocol defined study visits and/or subject withdraws consent/ assent (Refer to Section 9.2.4 for study medication discontinuation or termination criteria).

In case of premature discontinuation from double-blind study participation, all efforts will be made to perform all Visit 10 (Week 24) assessments. For premature discontinuations occurring in the OLE, all efforts will be made to perform all OLE Visit 6 assessments. The date the subject is withdrawn from the study and the reason for discontinuation must be recorded in the subject's electronic case report forms (eCRFs). All withdrawn subjects with ongoing AEs will be followed until the event has resolved or stabilized, until the subject is referred to the care of a local health care professional, or until a determination of a cause unrelated to the study medication or study procedures is made.

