9.2.4.2 Study Medication Discontinuation

Study medication should be permanently discontinued in the event of any of the following:

- Severe infection requiring parenteral antimicrobial therapy or hospitalization
- Symptomatic herpes zoster
- Malignancy – except for non-melanoma skin cancer (SCC or BCC) not in or near the treatment area
- Anaphylactic or severe allergic reaction
- WBC Count: $< 1 \times 10^9/L$ or second occurrence of $< 2 \times 10^9/L$
- ANC: $< 0.5 \times 10^9/L$ or second occurrence of $< 1 \times 10^9/L$
- Lymphocyte count: $< 0.3 \times 10^9/L$ or second occurrence of $< 0.5 \times 10^9/L$
- Platelet count: $< 50 \times 10^9/L$ or second event of $< 75 \times 10^9/L$ - in each case, value should be confirmed by retesting before treatment discontinuation

- Hemoglobin: < 6.5 g/dL or second occurrence of < 8 g/dL - in each case, value should be confirmed by retesting before treatment discontinuation
- AST or ALT:
 - > 5 x ULN persisting for 2-weeks of study medication interruption or second event of > 5 x ULN
 - > 3 x ULN with total bilirubin > 2 x ULN or symptoms of hepatocellular injury (fatigue, nausea, vomiting, right upper quadrant pain or tenderness, fever, rash and/ or eosinophilia (>5%).
- Serum creatinine: > 2 x ULN persisting for > 2 weeks of treatment discontinuation or second occurrence of > 2 x ULN

The continued treatment of subjects who experience other serious or severe adverse events considered related to study treatment should be discussed with the Sponsor's medical monitor.

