#### **Double-blind (DB) Period:**

A total of 120 subjects will be randomized in a 1:1:1 ratio:

- Vehicle Topical Solution BID for 24 weeks (6 months)
- ATI-50002 Topical Solution, 0.12%, BID for 24 weeks (6 months)
- ATI-50002 Topical Solution, 0.46%, BID for 24 weeks (6 months)

During the screening period, subjects will be assessed for eligibility into the study. Subjects will apply up to 4 mL of study medication to the entire scalp or patchy areas with a ½” margin twice a day for 24 weeks. Assessment of response to treatment will be performed at Week 4 (Visit 5), Week 8 (Visit 6), Week 12 (Visit 7), Week 16 (Visit 8), Week 20 (Visit 9), Week 24 (Visit 10), and post-treatment Week 28 (Visit 11). Safety and tolerability will be evaluated at each study visit by assessment of adverse events and vital signs, and at select visits, ECGs and clinical laboratory tests will be completed. The primary analysis will be conducted after all subjects complete Visit 10 or Visit 11 of the double-blind period.

Subjects who complete Visit 10 or Visit 11 (Week 24 or 28) will be eligible to enter a 28 week OLE. Subjects who decline or are not eligible for the OLE should be seen for the Visit 11 (Post-treatment) assessments.

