#### **4.3. PER PROTOCOL (PP) POPULATION**

The Per-Protocol (PP) population is defined as all subjects who are randomized and do not have any major protocol violations. Major protocol violations that will lead to exclusion from the PP are defined as:

1. Inclusion or Exclusion criteria not met
2. Concomitant medications taken during the study that interfere with efficacy
3. Did not apply at least 75% of study medication

4. Did not complete Week 24 (Visit 10).

This population will be used for supportive analyses of key efficacy analyses.

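### The SAP's compliance percentage ignores every day after the last dose; if it is used for the 75% Per-Protocol criterion, early stoppers who still have a Visit 10 can pass

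*SAP*

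**What the plan says.** SAP 3.3.6 defines compliance from the subject's own application regimen: exposure days minus the "number of days with less than the subject-specific expected number of applications) / (study medication exposure days)] x 100". Exposure in the double-blind period is "date of last DB dose – date of first dose + 1". The same section fixes the end point by actual use, not by plan: "Last Dose of Study Medication is defined as the last date that the subject applied study medication". Planned treatment is 24 weeks in each arm (SAP 1.1).

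Protocol 11.2 and SAP 4.3 list the same four grounds for exclusion from the PP population. The third is "Did not apply at least 75% of study medication". It has no denominator and no reference to the compliance formula. The fourth is failure to complete the Week 24 visit (Visit 10), and it is not tied to a study day.

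Two protocol passages bear on who can have a Visit 10 after stopping drug. Section 9.2.4.2 says "Study medication should be permanently discontinued in the event of any of the following" and does not say whether the subject also leaves the study. Section 5.9 says that after premature discontinuation from the double-blind period "all efforts will be made to perform all Visit 10 (Week 24) assessments".

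**The concern.** A PP analysis is meant to show the effect in subjects who received the treatment largely as planned. A compliance measure whose denominator stops at the last dose cannot detect a shortened course. It measures how regularly a subject applied drug while still applying it. If that measure is used for the third PP criterion, a subject treated for two weeks can pass, while one who used drug for the full 24 weeks with 26% short days fails.

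Protocol 11.4.2 names the PP analysis as a sensitivity analysis of the primary endpoint. SAP 5.2.3 runs it with LOCF, with observed data, and in the exploratory model by duration of episode. Safety-driven stops under Protocol 9.2.4.2 need not be balanced across arms, so retaining such subjects could affect the arms unequally. If the denominator were settled only after unblinding, the sensitivity analysis would lose much of its value.

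**Working it through.** **Inputs**
- Compliance (SAP 3.3.6): C = (E − S) / E × 100, where E is exposure days and S is the number of days below the subject's expected applications.
- E = date of last double-blind dose − date of first dose + 1 (SAP 3.3.6). A last dose on Day d gives E = d.
- Planned treatment: 24 × 7 = 168 days. This agrees with the schedule, which puts Visit 10 on Day 169, the day after 168 days of treatment.
- PP threshold: 75% (SAP 4.3).
- Week 24 analysis window: Days 155 to 182 (SAP Table 1).

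The documents print no compliance figure to reproduce.

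**Step 1: no short days (S = 0).** C = d/d = 100% for every stopping day. The share of planned days is d/168.

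| Last dose | SAP formula | Share of planned days |
|---|---|---|
| Day 15 | 15/15 = 100% | 15/168 = 8.9% |
| Day 60 | 60/60 = 100% | 60/168 = 35.7% |
| Day 84 | 84/84 = 100% | 84/168 = 50.0% |
| Day 112 | 112/112 = 100% | 112/168 = 66.7% |
| Day 126 | 126/126 = 100% | 126/168 = 75.0% |

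**Step 2: where the two measures part.** 0.75 × 168 = 126. With no short days, anyone whose last dose is before Day 126 is below 75% of plan but scores 100%. With 169 planned days the product is 126.75, which moves the cut to Day 127.

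**Step 3: with short days.** A last dose on Day 56 with 14 short days gives (56 − 14)/56 = 75.0%, a pass, but 42/168 = 25.0% of plan. A subject dosed to Day 168 with 44 short days (44/168 = 26.2%) scores (168 − 44)/168 = 73.8% and fails.

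**Step 4: an alternative reading.** Suppose days without application after the stop were subtracted as short days. The denominator still ends at the last dose, so a Day 60 stop gives (60 − 108)/60 = −80%. That reading does not rescue the definition.

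**Step 5: who could reach the PP population.** The fourth criterion removes anyone without a completed Visit 10, whatever the compliance score. Two routes remain.
- *Off drug, still attending.* Protocol 9.2.3 states that subjects with the listed ECG findings stop drug and are withdrawn. Section 9.2.4.2 mentions only the drug. A subject who stops under 9.2.4.2 and still attends Visit 10 meets the fourth criterion.
- *Exit visit recorded as Visit 10.* Section 5.9 seeks the Visit 10 assessments at early exit, and SAP 3.3.6 takes Study Visit as the nominal CRF visit. An exit visit on Day 60 belongs to the Week 8 window (Days 43 to 70) for analysis, yet it might count as a completed Visit 10. LOCF (SAP 3.3.4) would then carry that value to Week 24 in the PP analysis.

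**The case against.** The arithmetic of the formula is not in dispute; its link to the PP population is. Several counter-arguments have force.

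- **The link to the third criterion is not written down.** Seventy-five percent of study medication could be read as planned medication, and early stoppers would then fail. The protocol also monitors compliance by bottle weight and recorded missed doses (7.4, 7.5). The SAP formula counts full days, not applications: once-daily use on 50 of 168 days scores (168 − 50)/168 = 70.2%, although (336 − 50)/336 = 85.1% of applications were made. This stands, and the PP part of the point is conditional because of it. Still, no other percentage is defined, so a programmer would probably use this one. If another was meant, the SAP needs to say so.
- **The fourth criterion does most of the work.** A reader might infer that subjects who stop after a few weeks stay in the PP population as a matter of course. The documents do not support that. Those who leave with no Visit 10 are excluded.
- **Section 9.2.4.2 is silent on withdrawal.** It does not say that subjects remain on study, and Section 5.9 cross-refers to 9.2.4. Continued attendance is possible, not stated.
- **Analysis windows already map exit assessments by study day.** SAP 3.3.7 does this for the efficacy summaries. The fourth criterion, however, names Visit 10 and does not invoke those windows.
- **Compliance while on treatment is a legitimate quantity.** SAP 5.1 reports study drug duration with it, so short exposure is visible. Calling Table 14.1.9 inflated would go too far; the row needs a label and a companion.

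**Conclusion.** The point holds in conditional form. It is certain that the SAP compliance percentage takes no account of days after the last dose: with no short days it is 100% for any stopping day, including Day 15 (8.9% of plan) and Day 60 (35.7%). Whether this admits early stoppers to the PP population rests on two assumptions: that this formula implements the 75% criterion, and that the subject is counted as having completed Visit 10. Under both, subjects who stop before Day 126 can be retained.

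The group is limited to those who stop drug but attend Visit 10, and possibly early leavers whose exit assessments are recorded as Visit 10. The documents do not give its size, so no effect on an estimate can be computed. A reader might infer that the primary result is at risk. It is not: that analysis uses the ITT population (Protocol 11.4.1, SAP 5.2.2), and PP is supportive. The change is still worth making, because it is cheap and PP is the protocol's named sensitivity analysis of the primary endpoint.

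**What to change.** Make these changes in the SAP before the unblinding described in SAP 3.4.1:

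1. **Third PP criterion.** State that it uses planned double-blind treatment days (168) as the denominator, with days after a permanent stop counted as not applied.
2. **Fourth PP criterion.** State that it requires a Visit 10 assessment within the existing Week 24 analysis window (Days 155 to 182), so that an early-termination visit before Day 155 does not count. This is still needed after the first change: an early leaver whose last dose falls between Day 126 (75.0% of plan) and Day 154 (154/168 = 91.7%) could pass the third criterion with no Week 24 assessment.
3. **Table 14.1.9.** Show percent of planned days next to the current measure, and label the current one compliance while on treatment.

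Do not require the subject to be on drug at Visit 10. That would exclude someone who stopped on Day 160 (160/168 = 95.2% of plan), and it would leave unclear the status of a subject on a permitted interruption.

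The cost is SAP wording and simple derivations from dose dates, applications per day and visit dates already collected. Because Protocol 11.2 carries the same criteria without these details, record them as clarifications in SAP Section 6. The downside is a slightly smaller PP population.
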